9.3.1.2 Moderate to Vigorous Physical Activity

The secondary endpoint defined for analysis is the percent change in MVPA (ie, minutes spent in moderate or vigorous activity) during flagged wake epochs and calculated as absolute change/baseline (eg, change MVPA [minutes]/baseline MVPA [minutes]). Data will be aggregated across the 7-day baseline to produce an average baseline measurement to minimize diurnal variability. Similarly, the Weeks 6 and 12 endpoints will be constructed by averaging across the study visit day measurement and the measurements for the 6 days prior.

9.3.1.3 Actigraphy Analyses

9.3.1.3.1 Main Analyses

A longitudinal mixed model, similar to that used for the primary analysis of 6MWD, will be used to describe the change from baseline in actigraphy, percent change in overall activity and MVPA, separately, over time. All subjects, including those who did not complete both treatment sequences, will be included in the model. A contrast will be calculated for Week 12 to compare the treatment groups with respect to percent change. The outcome variable will be percent change from baseline. Analyses will be conducted on the FAS and the PPROT.

9.3.1.3.2

[REDACTED]

[REDACTED]

[REDACTED]

[REDACTED]

[REDACTED]

[REDACTED]

9.3.1.3.3 [REDACTED]

9.3.2 Borg Dyspnea Score

The Borg dyspnea score is an 11-point scale measuring the degree of dyspnea from 0 (no shortness of breath) to 10 (maximal shortness of breath). A score of 10 will be assigned to subjects who died or were too ill to walk for the 6MWT. Descriptive statistics of the raw and change from baseline values for Borg dyspnea score will be presented for each scheduled visit by treatment. Additionally, boxplots presenting the raw values and changes from baseline for each visit will be presented. The Borg dyspnea score will be treated as a continuous variable.

A longitudinal mixed model, similar to that used for the primary analysis of 6MWT, will be used to describe the change from baseline in Borg dyspnea score over time. All subjects, including those who did not complete both treatment sequences, will be included in the model. A contrast will be calculated for Week 12 to compare the treatment groups with respect to change. The outcome variable will be change from baseline. Independent variables will be treatment, the subject's baseline Borg dyspnea score, treatment sequence, visit number, and the interaction of visit and treatment. Analyses will be conducted on the FAS and the PPROT.

9.3.3 6MWD and Borg Dyspnea Composite Score

The intent of the 6MWT is to determine how much exercise subjects can do during the course of carrying out activities of daily living. However, the capacity of subjects to function is determined not only by what they can do when they exert themselves to the fullest, but also by how they feel when they are carrying out their usual activities of daily living. It is important not only to look at the distance traversed during the unencouraged 6MWT, but also the symptoms experienced at the end of the effort (Rao 2019).

The 6MWD and Borg dyspnea composite score is derived based on the results of the 6MWD and the Borg dyspnea scale measuring the degree of dyspnea. The following derivation strategy will be employed to calculate the 6MWD and Borg dyspnea composite score:

[REDACTED]

Descriptive statistics of the raw and change from baseline values for composite score will be presented for each scheduled visit by treatment. The composite score will be treated as a continuous variable. A longitudinal mixed model, similar to that used for the primary analysis of 6MWD, will be used to describe the change from baseline in the composite score over time. All subjects, including those who did not complete both treatment sequences, will be included in the model. A contrast will be calculated for Week 12 to compare the treatment groups with respect to change.

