#### 10.2 SAMPLE SIZE

This is an adaptive design study that will be initiated as a crossover study (the **Original Crossover Design**). However, due to the uncertainty of clinical benefit with inhaled treprostinil exposure in PH-COPD subjects and the ongoing COVID-19 pandemic, there is a possibility of treatment discontinuations and/or missing data due to COVID-19 impeding onsite visits, which may render estimates for efficacy outcomes inefficient or biased, thus an automatic switch to the **Contingent Parallel Design** or an alternative primary endpoint that has been incorporated in this study protocol. The protocol specifies the algorithm to seamlessly transition to a parallel-group design (**Contingent Parallel Design**) if the degree of missing data subsequent to subject treatment crossover is not tolerable for primary analysis.

Similarly, this protocol specifies the algorithm to switch the primary endpoints to measurements conducted remotely if the COVID-19 pandemic prevents onsite visits and data collection for the intended primary endpoint data. Evaluations of missing data will be performed in a blinded fashion at the conclusion of the study, irrespective of actual efficacy outcomes and any information regarding efficacy outcomes prior to crossover and, as such, will not impact the Type I error rate (FDA Guidance 2019). Section 10.2.1 presents the adaptation procedures to be employed for this protocol.

The **Original Crossover Design** is a 2x2 crossover study designed to have 90% power to detect a placebo-corrected mean change from baseline difference of 30 meters, assuming that the standard deviation of differences is 85 meters and using a 2-group t-test with a 0.01 two-sided significance level, with a sample size of 124 subjects (62 in each sequence group). To account for a discontinuation rate of approximately 10%, the total sample size will be approximately 136 subjects.

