7.4 COVARIATES

Efficacy analyses will include the assigned treatment sequence and period order as covariates. Change from baseline analyses will include the baseline measurement as a continuous covariate.

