9.1.2 Primary Efficacy Analysis Data

The primary efficacy analysis will be based on all available measurements of the 6MWD for the FAS as observed in the study, with the exception that for subjects whose 6MWD measures at Week 6 or Week 12 of either Period are missing due to death or being too ill to perform 6MWT, the missing values will be imputed as the worst possible score (0 meter) and change-from-baseline scores calculated. For missing data due to any other reason, the missing value will not be imputed.

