9.3.4 NT-proBNP

Descriptive statistics of the raw values for NT-proBNP will be presented for each scheduled visit by treatment. Because the parameter is highly skewed, the data will be log-transformed before analysis. A mixed model will be used to describe log NT-proBNP over time. The outcome variable will be the value at each time of measurement, not the change from baseline.

Independent variables will be treatment, treatment sequence, the subject's baseline log NT-proBNP, visit number, and the interaction of visit and treatment. A contrast will be calculated at Week 12 to compare the treatment with respect to level of the parameter.

The contrast will be on the log scale. In order to provide summary statistics that are easily clinically interpretable, the estimates may be back transformed to the natural scale and the change from baseline may be calculated as the difference between the mean of the back-transformed estimates and the mean of the baseline value.

Observed values for the FAS and PPROT will be used with no imputation for missing values. However, if a NT-proBNP value is reported below the lower limit of quantification, half of the lower limit of quantification will be used for summary and analysis (eg, if the result is reported as '<51 ng/L,' a numerical value of 25 ng/L will be used).

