9.4 OTHER SECONDARY EFFICACY MEASURES

9.4.1 St. George's Respiratory Questionnaire

The SGRQ is a 50-item questionnaire designed to measure impact on overall health, daily life, and perceived wellbeing in patients with obstructive airways disease (Jones 1992). Scores for the SGRQ are totaled into 3 components (symptoms, activities, impacts) as well as a total score. Scores weighted and expressed as a range from 0 to 100, with higher scores indicating more limitations. The current established minimal important difference for SGRQ scores in an average COPD population is -4 units (Jorrit 2015). Calculation of component and total scores are described in the manual (Jones 2009).

Descriptive statistics for the raw and change from baseline to Week 12 values for the SGRQ the components and the total score will be presented for each scheduled visit by treatment.

Additionally, boxplots presenting the raw values and changes from baseline for each visit will be presented. The SGRQ scores will be treated as a continuous variable.

A longitudinal mixed model will be used to describe the change from baseline for the each of the scores over time. All subjects, including those who did not complete both treatment sequences, will be included in the model. A contrast will be calculated for Week 12 to compare the treatment groups with respect to change. The outcome variable will be change from baseline. Independent variables will be treatment, the subject's baseline average SGRQ score, treatment sequence, visit number, and the interaction of visit and treatment.

Observed values for the FAS and PPROT will be used with no imputation for missing values.

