9.4.2 University of California San Diego Shortness of Breath Questionnaire

The UCSD SOBQ is a self-administered rating of dyspnea associated with activities of daily living (Eakin 1998). The questionnaire contains 24 items on a 6-point scale, where 0 = "not at all" and 5 = "maximal or unable to do because of breathlessness" and total score are summed across items for a range from 0 to 120. The current established minimal important difference for UCSD SOBQ scores in a chronic lung disease population is 5 units (Ries 2005). Descriptive statistics of the raw and change from baseline to Week 12 values for the UCSD SOBQ score will be presented for each scheduled visit by treatment.

A longitudinal mixed model will be used to describe the change from baseline in the total score over time. All subjects, including those who did not complete both treatment sequences, will be included in the model. A contrast will be calculated for Week 12 to compare the treatment groups with respect to change. The outcome variable will be change from baseline. Independent variables will be treatment, the subject's baseline average UCSD SOBQ score, treatment sequence, visit number, and the interaction of visit and treatment.

Observed values for the FAS and PPROT will be used with no imputation for missing values.

9.4.3

[REDACTED]

[REDACTED]

[REDACTED]

[REDACTED]

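### The crossover model lists for Borg, NT-proBNP, SGRQ and UCSD SOBQ omit the period term that SAP 7.4 requires and leave visit number undefined; the likely cost is small and mainly lost precision

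*SAP*

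**What the plan says.** The general rule in SAP 7.4 is "Efficacy analyses will include the assigned treatment sequence and period order as covariates", with the baseline value added for change-from-baseline analyses.

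Four endpoint sections then give their own lists of independent variables:
- Borg (SAP 9.3.2): treatment and the subject's "baseline Borg dyspnea score, treatment sequence, visit number, and the interaction of visit and treatment".
- NT-proBNP (SAP 9.3.4): treatment, sequence, and the subject's "baseline log NT-proBNP, visit number, and the interaction of visit and treatment".
- SGRQ (SAP 9.4.1): treatment and "baseline average SGRQ score, treatment sequence, visit number, and the interaction of visit and treatment".
- UCSD SOBQ (SAP 9.4.2): treatment and "baseline average UCSD SOBQ score, treatment sequence, visit number, and the interaction of visit and treatment".

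Each list has one of the two terms named in 7.4 (sequence) and lacks the other (period). Each section asks for a treatment contrast at Week 12. None says whether visit number counts visits within a period or across the whole study. SAP 9.1.2 uses the within-period labelling when it speaks of "6MWD measures at Week 6 or Week 12 of either Period are missing".

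The Borg section also states "All subjects, including those who did not complete both treatment sequences, will be included in the model", and the SGRQ and UCSD SOBQ sections say the same. Under SAP 9.3 Borg and NT-proBNP are in the ordered formal testing. Under SAP 7.7 SGRQ and UCSD SOBQ are not formally tested.

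**The concern.** In a 2x2 crossover the period term separates a general shift between Period 1 and Period 2 from the treatment effect. Here a general rule and four specific lists disagree. A programmer who follows 7.4 fits period, and one who follows the lists does not.

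Without period, a period effect has two consequences. First, active-minus-placebo differences are shifted in opposite directions in the two sequences, which adds to the residual variance. Second, if more subjects are lost before or during Period 2 in one sequence than in the other, the shifts no longer cancel and part of the period effect is read as treatment. For Borg and NT-proBNP this touches formal tests; for the two questionnaires it touches estimates only.

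**Working it through.** **1. The plan's own figure.** Protocol 10.2 and SAP 5.1 plan 124 subjects (62 per sequence) for a 30 m effect on 6MWD, SD of differences 85 m, two-sided α = 0.01, 90% power. The standard error is 85/√124 = 7.63 m and the noncentrality is 30/7.63 = 3.93. A noncentral t with 122 degrees of freedom gives power 90.3%, so the figure reproduces. It already rests on a period-adjusted comparison: a two-group t-test between sequences on within-subject period differences.

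**2. Precision without a period term.** Let π be the Period 2 minus Period 1 effect on the analysed outcome. The expected active-minus-placebo difference is τ − π in the active-first sequence and τ + π in the placebo-first sequence. Pooling them without period raises the variance from SDdiff² to SDdiff² + π², so

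SE multiplier = √(1 + (π/SDdiff)²).

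| π/SDdiff (assumed) | SE multiplier | Power at the 6MWD design inputs |
|---|---|---|
| 0 | 1.00 | 90.3% |
| 0.25 | 1.03 | 88.2% |
| 0.5 | 1.12 | 81.4% |
| 1.0 | 1.41 | 56.6% |

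The power column borrows the 6MWD inputs, since the documents give no SD for the four endpoints. It shows scale only.

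**3. Bias without a period term.** Let d₁ and d₂ be the Period 2 losses in the active-first and placebo-first sequences. Among complete pairs the mean difference is τ + π(d₁ − d₂)/(2 − d₁ − d₂). That is the upper bound on the leak: 0.10/1.80 = 5.6% of π at 15% v 5%, 0.15/1.75 = 8.6% at 20% v 5%, 0.20/1.80 = 11.1% at 20% v 0%. A mixed model also uses subjects with Period 1 data only, which reduces the leak. An exact generalised least squares expectation (68 per sequence, two visits per period, within-period correlation 0.8, between-period correlation 0 to 0.7, all assumed) gives:
- equal loss: 0
- 15% v 5%: 3.0 to 5.1% of π
- 20% v 5%: 5.0 to 8.3% of π
- 20% v 0%: 6.1 to 10.3% of π
- 30% v 10%: 10.9% of π at correlation 0.7

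The sign depends on which sequence loses more. With period in the model the bias is zero in every case.

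In standard-error units: at 20% v 10% loss and correlation 0.36 the leak is 4.3% of π. With π = 0.25 SDdiff that is 0.043 × 0.25 = 0.011 SDdiff, against a design standard error of 1/√124 = 0.090 SDdiff, so about 0.12 of a standard error.

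**4. Type I error.** In a simulation (500 replicates per setting, so noisy), rejection under the null at α = 0.05 without period was 0.2 to 2% at π = 1 SDdiff. At that size the omission is conservative.

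**5. What visit number could mean.** There are eight sequence-by-period-by-visit cells.
- Visit as Week 6/12 within period: five columns, rank 5, and period is absent. Adding period gives six columns, rank 6, all estimable.
- Visit as Weeks 6, 12, 19 and 25: visit with visit-by-treatment already has rank 8. Adding the listed sequence term gives nine columns at rank 8, so sequence is aliased. A Week 12 contrast alone is not estimable. The average of the Week 12 and Week 25 contrasts is: its cell weights are +½ and −½ for active-first at Weeks 12 and 25, and −½ and +½ for placebo-first, so sequence and period both cancel.

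**The case against.** Five points are made on the other side.

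- **SAP 7.4 has no exceptions, and the lists do not claim to be exhaustive.** Appendix 12.4.4 removes sequence and period for the parallel design by amending 7.4, so 7.4 works as the governing rule. Appendix 12.4.6 still lists sequence for the parallel SGRQ and UCSD SOBQ models, which suggests loose drafting rather than a decision to drop period. This stands: the lists may be incomplete rather than wrong. The remedy is the same.
- **The Borg model is described as similar to the primary one, whose terms in SAP 9.1.3 are redacted.** This stands too. The redaction cannot show whether period is carried over to Borg, although Borg's own visible list lacks it.
- **A reader might infer that no meaning of visit number gives a valid crossover analysis.** That goes too far. With four study-week visits, the average of the Week 12 and Week 25 contrasts is the period-adjusted crossover comparison. What is missing is a statement of that contrast.
- **A reader might infer that disease drift over 25 weeks passes straight into these models.** SAP 7.1 gives each period its own baseline, so a steady drift produces the same 12-week change in both periods. Because baseline is also a covariate, a part remains. With an assumed between-to-within SD ratio of 2:1 the baseline slope is 4/(4 + 1) = 0.8, so about 0.2 of one period's drift survives. A difference between periods in the change itself is not removed.
- **The correlation of 0.36 is not given by the plan.** It comes from 1 − 85²/(2 × 75²), but footnote 2 to SAP 5.1 says the 85 m was chosen as a more conservative value for the smaller design. The two SDs are separate planning assumptions, and both are for 6MWD. The working therefore uses a range of 0 to 0.7.

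**Conclusion.** The conflict between SAP 7.4 and the four lists is real. If the lists are followed with visit as Week 6/12, the analysis is less precise than the one 7.4 promises whenever there is a period effect: 3% on the standard error at π = 0.25 SDdiff, 12% at 0.5. About 3 to 11% of π enters the contrast when Period 2 loss differs by 10 to 20 percentage points between sequences, and none when loss is equal.

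These sizes rest on assumed period effects, losses and correlations. Period-specific baselines make a large π less likely where the only cause is steady drift.

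A reader might infer that the formal Borg and NT-proBNP tests are materially biased or have inflated Type I error. The documents and the calculations do not support that: the leak is a small share of an unknown effect, and the main consequence is lost power. This is a small improvement, worth making because two formally tested endpoints are left with two conflicting specifications.

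**What to change.** For the Original Crossover Design only, in SAP 9.3.2, 9.3.4, 9.4.1 and 9.4.2:
- Add period to the list, so that it reads treatment, period, sequence, visit, visit-by-treatment and baseline, in agreement with 7.4.
- Define visit as the within-period visit (Week 6 or Week 12 of each period).
- Define the Week 12 contrast as the period-adjusted treatment difference at the second visit of each period.

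The cost is wording in four sections and one degree of freedom per model. No new data are needed. The change should be made before unblinding.

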9.3.4 NT-proBNP

Descriptive statistics of the raw values for NT-proBNP will be presented for each scheduled visit by treatment. Because the parameter is highly skewed, the data will be log-transformed before analysis. A mixed model will be used to describe log NT-proBNP over time. The outcome variable will be the value at each time of measurement, not the change from baseline.

Independent variables will be treatment, treatment sequence, the subject's baseline log NT-proBNP, visit number, and the interaction of visit and treatment. A contrast will be calculated at Week 12 to compare the treatment with respect to level of the parameter.

The contrast will be on the log scale. In order to provide summary statistics that are easily clinically interpretable, the estimates may be back transformed to the natural scale and the change from baseline may be calculated as the difference between the mean of the back-transformed estimates and the mean of the baseline value.

Observed values for the FAS and PPROT will be used with no imputation for missing values. However, if a NT-proBNP value is reported below the lower limit of quantification, half of the lower limit of quantification will be used for summary and analysis (eg, if the result is reported as '<51 ng/L,' a numerical value of 25 ng/L will be used).

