7.1 BASELINE

Given the crossover design utilized for this study, Periods 1 and 2 each have a different baseline for efficacy measurements: Period 1: Day 1 and Period 2: Week 14. With the exception of actigraphy measurements, the baseline value will be defined as the non-missing value immediately prior to dosing with study drug for Period 1: Day 1 and Period 2: Week 14. The baseline period for actigraphy measurements will be the last 7 days during the washout period prior to the day of dosing on Day 1 and Week 14. In the event that the washout period is less than 7 days then only the non-dosing days will be used to derive a baseline average.

For safety evaluations, the baseline will be defined as the last evaluation closest, but prior to, the first dose of study drug during the low dose run-in period.

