7.2 CHANGE FROM BASELINE

For parameters measured at baseline, the variables of interest are the change from baseline of the original measurements. Unless otherwise specified, all changes from baseline (for all variables where this is applicable) will be calculated as follows:

$$\text{Change from baseline} = \text{Post baseline} - \text{baseline}$$

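### The optional NT-proBNP change from baseline in SAP 9.3.4 subtracts an arithmetic baseline mean from a geometric-type mean, so both arms show a fall when nothing has changed

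*SAP*

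**What the plan says.** SAP 9.3.4 gives the reason for the log scale: "Because the parameter is highly skewed, the data will be log-transformed before analysis". The mixed model is fitted to log NT-proBNP, with a covariate list that includes "baseline log NT-proBNP, visit number, and the interaction of visit and treatment". On the outcome it is explicit: "The outcome variable will be the value at each time of measurement, not the change from baseline". The Week 12 contrast stays on the log scale.

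For summaries that clinicians can read, the section lets the estimates be back-transformed and adds that "the change from baseline may be calculated as the difference between the mean of the back-transformed estimates and the mean of the baseline value". Both steps are permissive (may).

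Four other places bear on this:

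- SAP 2.4 names the endpoint as the change in NT-proBNP from Baseline to Week 12. SAP 9.3 puts it among the endpoints tested formally in order and defines a decrease as improvement.
- SAP 7.1 defines the baseline value as the observed measurement just before dosing, and under the crossover "Periods 1 and 2 each have a different baseline for efficacy measurements".
- SAP 7.2 sets the general rule: "Unless otherwise specified, all changes from baseline (for all variables where this is applicable) will be calculated as follows", that is, post-baseline minus baseline.
- Appendix 12.4 changes only the sections it names, and 9.3.4 is not one of them. The text therefore applies under both the crossover and the parallel design.

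**The concern.** Exponentiating a mean estimated on the log scale gives a geometric-type mean. The term subtracted from it is described only as the mean of the baseline value. Section 9.3.4 writes log when it means the log baseline, and 7.1 makes the baseline value an observed concentration. The natural reading of the second term is therefore an arithmetic mean in ng/L. Both terms carry the same unit but are different kinds of mean, and for a skewed marker the arithmetic one is larger.

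The subtraction then gives a negative number with no true change, in the direction the SAP defines as improvement. This is the only change formula that 9.3.4 provides. For descriptive output it says "Descriptive statistics of the raw values for NT-proBNP will be presented for each scheduled visit by treatment", whereas for Borg the plan is "Descriptive statistics of the raw and change from baseline values for Borg dyspnea score will be presented for each scheduled visit by treatment", and the composite score, SGRQ, UCSD SOBQ and PGA are treated in the same way as Borg. If the option is used, this figure is the one a clinical reader is likely to take as the size of the NT-proBNP change.

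**Working it through.** **Inputs.** From the documents: the marker is highly skewed, the model is on the log scale, and the derived change is as quoted from 9.3.4. The documents give no log-scale SD (s), no correlation between baseline and Week 12 log values (r), and no NT-proBNP effect or power figure, so there is no stated result to reproduce. Assumptions: lognormal values, no true change, s from 0.3 to 1.2, and r of 0.7, 0.8 or 0.9.

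**Direction.** For any positive variable that is not constant, the geometric mean is below the arithmetic mean. The sign therefore does not depend on the lognormal assumption. Only the size does.

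**Reading A: back-transformed LS mean minus arithmetic baseline mean.** With log mean m, the geometric mean is exp(m) and the arithmetic mean is exp(m + s²/2). As a share of the arithmetic baseline mean, the change reported under no true change is

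exp(−s²/2) − 1.

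For s = 1.0 this is exp(−0.5) − 1 = −39.3%.

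**Reading B: each subject's predicted log value is exponentiated, then averaged.** Predictions from the baseline covariate have log variance r²s², so their mean after exponentiation is exp(m + r²s²/2). The reported change is

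exp(−(1 − r²)s²/2) − 1.

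For s = 1.0 and r = 0.8 this is exp(−0.36/2) − 1 = −16.5%.

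False fall, as % of the arithmetic baseline mean:

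| Log SD | Reading A | B, r = 0.7 | B, r = 0.8 | B, r = 0.9 |
|---|---|---|---|---|
| 0.3 | 4.4 | 2.3 | 1.6 | 0.9 |
| 0.5 | 11.8 | 6.2 | 4.4 | 2.3 |
| 0.8 | 27.4 | 15.1 | 10.9 | 5.9 |
| 1.0 | 39.3 | 22.5 | 16.5 | 9.1 |
| 1.2 | 51.3 | 30.7 | 22.8 | 12.8 |

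**Simulation checks with no true change.** These use one post-baseline visit per period, which is simpler than the planned repeated-measures model, and a correlation of 0.8.

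- Parallel, 133 per arm, 4,000 trials, the five SDs in order. Reading A: −4.4%, −11.6%, −27.3%, −39.1%, −50.8%. Reading B: −1.6%, −4.3%, −10.8%, −16.2%, −22.2%.
- Crossover, 124 subjects with period-specific baselines, 2,000 trials, known covariance. Reading A: −4.4%, −11.8%, −27.2%, −39.0%, −50.9%.
- A separate crossover run (124 subjects, 2,000 trials, assumed geometric mean 500 ng/L, s = 1.0) gave Reading A changes of −322 ng/L on placebo and −320 ng/L on treprostinil. The arithmetic baseline mean was about 824 ng/L. Both arms fell in every trial.
- If the predictions also use each subject's own post-baseline data, the false fall at s = 1.0 shrinks to about 12%. It does not vanish.

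**A real rise can be hidden.** Take s = 1.0, a geometric mean of 500 ng/L and a true 20% rise on treprostinil. Reading A gives 500 × 1.2 − 500 × exp(0.5) = 600 − 824 = −224 ng/L. The simulation gave −225.

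**Same kind of mean in both terms.** The ratio of the back-transformed LS mean to the pooled geometric baseline mean gave a null change of 0.0% to +0.4% (parallel) and 0.0% to +0.2% (crossover).

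**The case against.** The strongest reply has four parts.

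1. **The wording is loose.** Speaking of a mean of back-transformed estimates suggests exponentiating first and averaging afterwards, since a back-transformed LS mean is already one number per arm and visit. That favours Reading B, or a version using post-baseline data, with a smaller false fall. This stands as a point about size. It does not rescue the formula, because every version examined still gives a fall. The artefact disappears only if the baseline term is a geometric mean, which the text does not say.

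2. **The sizes are assumed.** This stands. A range from about 1% to 51% establishes the direction and shows that the effect need not be small. It does not predict the figure in this trial.

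3. **The step is optional.** If it is not used, the general rule in SAP 7.2 remains available, and an NT-proBNP change table may be planned in the list of tables, which is not in the text available. This stands too. However, the permissive wording governs whether the figure is produced, not whether it would be right.

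4. **No trial conclusion changes.** The log-scale contrast, its p-value and the ordered test are untouched. The artefact is common to both arms and does not favour treprostinil over placebo. The planned means, medians and quartiles of raw values by visit would let a careful reader notice the mismatch. All of this is right, and it limits how serious the point is.

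**Conclusion.** The concern holds: the formula is wrong as written. On its plain reading it mixes a geometric-type mean with an arithmetic mean and produces a fall in both arms when nothing has changed. The direction follows from the skewness the SAP itself states. The size rests on assumed values: 4% to 51% of the arithmetic baseline mean for log SD 0.3 to 1.2, or 1% to 31% if baseline-based predictions are averaged.

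The consequence is limited to a descriptive within-arm change, and only if the option is used. Extra noise in the between-arm difference of these figures would arise only if each arm's own baseline mean were subtracted. The text does not specify that, so it is not part of the finding. The sentence should be corrected, but it does not threaten the formal NT-proBNP test.

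**What to change.** Replace the sentence in SAP 9.3.4 so that both terms are the same kind of mean:

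- For each arm, report the ratio to baseline, exp(LS mean of log NT-proBNP at Week 12 − pooled mean log baseline), where the pooled mean is the value at which the LS means are evaluated. Under the crossover it runs over both period baselines (Day 1 and Week 14). Under the parallel design it is Day 1 only.
- Report exp(treatment contrast) with its confidence interval as the geometric mean ratio.
- If a change in ng/L is wanted, subtract the geometric mean of that same pooled baseline from the back-transformed LS mean. This keeps the SAP's aim of a figure in natural units.

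The cost is one sentence, with the same model and the same data. Where the option would have been used, the reported within-arm changes will look less favourable than under the present wording.
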